 - b. Compared to no treatment, Norditropin will significantly reduce markers of hepatocellular injury and steatohepatitis, including transaminases, gamma glutamyl transferase (GGT), and cytokeratin -18 (CK18).
2. **Physiologic replacement of GH with Norditropin will be neutral to glucose homeostasis and will improve other measures of cardiometabolic risk.**
 - a. Fasting and 2-hour glucose, HOMA-IR, and Matsuda index will not be significantly different from baseline after 24 weeks of Norditropin treatment
 - b. Norditropin will result in a reduction in VAT (measured by MRI) and trunk fat (measured by DXA) compared to no treatment
 - c. Norditropin will result in an increase in adiponectin and a reduction in CRP compared to no treatment

III. Subject Selection

24 obese young adults (M and F) with liver fat $\geq 5\%$ on ^1H -MRS and relative reduction in GH but without a known clinical diagnosis of growth hormone deficiency will be recruited for the RCT. We anticipate screening up to 150 subjects to identify 24 who meet enrollment criteria. Relative reduction in GH will be assessed by IGF-1 z-score, with subjects whose IGF-1 z-scores are ≤ 0 eligible for the study. Many previous studies have defined relative GH deficiency as an IGF-1 z-score ≤ 0 (68, 69).

Inclusion criteria:

1. Males and Females ages 18-29yo
2. BMI $\geq 95^{\text{th}}$ percentile and/or $\geq 30\text{kg}/\text{m}^2$
3. Hepatic fat $\geq 5\%$ by ^1H -MRS
4. IGF-1 standard deviation score (SDS) ≤ 0

Exclusion criteria:

1. Alcohol consumption of >14 drinks per week (F) or >21 drinks per week (M) (40)
2. Use of insulin or oral anti-diabetic medications, or HbA1c $>7\%$ or fasting glucose $\geq 126\text{mg}/\text{dL}$
3. Use of corticosteroid, gonadal steroids, or methotrexate ≤ 3 months prior to baseline visit
4. Known diagnosis of alpha-1 antitrypsin deficiency, Wilson's disease, hemochromatosis, or autoimmune hepatitis
5. HgB < 11.0 g/dL or wt $< 50\text{kg}$
6. AST or ALT $>2.5\text{x}$ upper limit of normal (ULN), total bilirubin $> \text{ULN}$, positive Hep B sAg, or Hep C Ab
7. Routine MRI exclusion criteria (including weight >450 lbs)
8. Use of weight-loss medications or previous weight loss surgery
9. Pregnant or breastfeeding, or, for sexually-active females, unwillingness to use an appropriate form of contraception during the study

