For all female subjects, urine pregnancy tests will be performed at all visits, and a positive pregnancy test will result in immediate discontinuation. At baseline, 12 weeks, and 24 weeks, subjects will be counseled regarding lifestyle modification (see Methods). Subjects will continue to receive care from their regular medical providers, including hepatologists, throughout the study. Any subject not under the care of a hepatologist who is found at screen to have $\geq 5\%$ liver fat and significantly elevated AST or ALT will be offered referral to the hepatology clinic.

Screen: (1) Informed consent; (2) Detailed H&P, including medications and alcohol habits; (3) blood sampling for IGF-1, CBC, HbA1c, fasting glucose, AST, ALT, total bilirubin, Hepatitis B sAg, Hepatitis C antibody; (4) ^1H -MRS/MRI of abdomen in fasting state for quantification of liver fat. (This scan will also be used to assess VAT and SAT for those eligible subjects participating in the baseline visit.)

Randomization and Study Drug: After the screening visit, eligible patients who wish to participate will be randomized in a 1:1 ratio to Norditropin vs. no treatment. The study will not be blinded and placebo will not be used to avoid daily injections without benefit for subjects randomized to no treatment. Randomization will be stratified by gender and Vitamin E use. The starting dose of Norditropin will be 0.5 mg daily, which is a recommended dose for restarting growth hormone in young adults with GHD during the transition from adolescence to adulthood (70). IGF-1 will be checked at 2, 4, 6, 12, and 18 weeks, and will be reviewed by the PI. Active dose adjustments will be performed per algorithm as follows. A 20% dose increase will be performed for any Norditropin subject with IGF-1 SDS ≤ 0 . Conversely, a 20% decrease in dose will be performed for any Norditropin subject with IGF-1 SDS > 2 .

| Norditropin Dosing Algorithm (starting dose 0.5 mg) | | |
|--|-------------------------------|---------------------|
| IGF-1 SDS ≤ 0 | $0 < \text{IGF-1 SDS} \leq 2$ | IGF-1 SDS > 2 |
| 20% dose increase | maintain dose | 20% dose reduction* |
| *Subjects with persistent IGF-1 SDS > 2 after 2 dose reductions will be discontinued from the study. | | |

Baseline Visit:

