Analysis will be intention-to-treat, using all available data from all subjects. Wilk-Shapiro test will be used to assess for normality of distribution of all variables, and variables that are not normally distributed will be appropriately transformed. Baseline variables will be compared between treatment groups, and any baseline variable that is statistically different between treatment groups will be adjusted for in subsequent analysis. Changes in variables measured only at baseline and 6 months, including the primary endpoint of liver fat, will be initially assessed using a two-sample t-test comparing mean changes between treatment groups. A critical alpha level of 0.05 will be used as the threshold for significance, and all statistical tests will be two-tailed. Subsequently, adjusted analyses will be performed including as covariates any baseline characteristics that differ between treatment groups and any differential changes in nutritional intake or physical activity between treatment groups over the study duration. For variables measured at ≥ 3 timepoints throughout the study (e.g., IGF-1, AST and ALT), we will analyze the longitudinal data using general linear mixed effects modeling, testing for time x treatment group interaction. The primary analysis will be an intention to treat analysis using all available data. We will consider secondary multiple imputation based analyses if necessary.

A supplementary analysis will be performed assessing stimulated growth hormone levels in response to Arginine testing. Using peak GH as the independent variable, we will assess the hypothesis that peak GH will be negatively associated with liver fat quantity.

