Sample Size and Power Calculations: The study is designed to yield pilot data, with the primary endpoint being change in hepatic fat fraction. As we do not have preliminary data on this measure in an adolescent population, we used a published standard deviation (SD) of 3.1%. A sample size of 24 subjects, with up to 20% discontinuation rate, yielding 19 evaluable patients, has 80% power to detect a 4.2 percentage point treatment effect on liver fat (e.g., a reduction from 7% liver fat to 2.8% liver fat), which is the minimum difference that would be clinically relevant, as absolute reductions of ≥ 4 -5% liver fat have been considered clinically relevant in previous publications (77, 78). For secondary variables of interest, the study is has 80% power to detect a treatment difference of approximately 1.4 SD.

VIII. Risks and Discomforts

Radiation: Subjects will have 2 DXA scans over 6 months, for a total radiation risk from both scans of 2 microSieverts. This radiation exposure is minimal and does not pose excessive risk to subjects. Female subjects must have a negative pregnancy test before DXA scanning.

Blood Drawing: Blood sampling volumes will be as follows: screen 27cc, baseline and 24 week visit 99cc, safety visits 5-8cc each (5 cc at 2 and 4 weeks, 8cc at 6, 12, 18 weeks). The total blood drawing will be 286cc over 6 months. The maximum blood drawn during any 8 week period (screen+baseline+2wk+4wk) will be no more than 140cc. Body weight ≥ 50 kg and Hgb ≥ 11 g/dL will be required to participate, which will ensure that the blood volume sampled is within guidelines and does not pose significant risk to subjects.

Blood drawing may cause discomfort, pain, and bruising.

MRI/MR spectroscopy: MRI and MR spectroscopy will be performed using FDA approved devices and pulse sequences, and there are no known foreseeable risks associated with exposure to MRI. Subjects will be carefully screened for the presence of metallic implants (e.g., vascular clamps) prior to MR scanning. Some

subjects report claustrophobia during MRI scans, and if any patient experiences discomfort during the scan, the procedure will be aborted and not repeated without the subject's consent.

Oral Glucose Tolerance Test: Oral glucose tolerance test has no significant risks. Some subjects may experience nausea or lightheadedness during the procedure, and supportive nursing care will be provided.

Clonidine/Arginine Stimulation:

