Possible side effects of rhGH include headache, edema, myalgia, arthralgia, and hyperglycemia. Subjects will be asked to contact study physicians right away with any potential side effects, and subjects who experience concerning side effects will be advised to discontinue the medication. A physician will be available on-call 24 hours/day, 7 days/week, to all study participants for any questions or concerns. Fasting blood sugar will be checked at 2, 4, 6, and 12 weeks, and any subject with a fasting blood sugar ≥ 126 mg/dL that is confirmed on recheck will be discontinued from the study, with appropriate follow-up to ensure return to euglycemia. RhGH, particularly at physiologic dosing, is incredibly well-tolerated in the pediatric population, and there were no significant GH-related side effects in our pilot study of obese adolescents. When side effects, including hyperglycemia, do occur with rhGH, these resolve with discontinuation of treatment unless there is an underlying, non-GH-related, etiology.

As stated elsewhere, a pregnancy test will be performed at each visit for females able to become pregnant, and subjects will be informed of the study-related risks of pregnancy and the need not to become pregnant during the study. If a subject is found to be pregnant, she will be asked to discontinue the study drug immediately, and the event will be reported to Novo Nordisk as below. She will be referred for continued primary care and OBGYN care.

Subjects will be carefully instructed regarding reconstitution, safe injection technique, and appropriate storage of the study drug and disposal of sharps. A study investigator will be on call 24/7 for any questions or concerns.

Persistent elevations in blood sugar after discontinuing growth hormone are not expected. However, if any subject is discontinued for fasting glucose ≥ 126 mg/dL, confirmed on repeat draw (see below), we will arrange for a repeat fasting glucose approximately 2-4 weeks after stopping growth hormone. We will arrange this to be performed either at MGH through the study or locally with the patient's primary care doctor. If this is still elevated, the patient will be referred to his/her primary care doctor for continued follow-up and, if desired, we will also arrange for follow-up with endocrinology at MGH.

Individual and Study Stopping Rules

Individuals will be discontinued from the study if

- s/he undergoes 2 dose reductions and continues to have IGF-1 SDS >2

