- s/he has fasting glucose ≥ 126 mg/dL confirmed on a repeat draw
- s/he reports significant adverse effects including significant arthralgia, myalgia, or edema

The study will be stopped if

- More than 2 individuals in the GH group have persistent fasting glucose ≥ 126 mg/dL

The study will be halted and the dosing algorithm reconsidered (and lowered) if

- More than 2 individuals in the GH group have IGF-1 SDS >2 after 2 dose reductions

Alternative Treatments

There are no FDA-approved highly effective treatments for NAFLD in young adults, and research into novel treatments is urgently needed. Vitamin E, ursodiol, and metformin are sometimes used for NAFLD, and vitamin E has been demonstrated to improve liver histology in individuals with NASH. Subjects who wish to participate and have been receiving Vitamin E or ursodiol at a stable dose for ≥ 6 months will be eligible for the study with continued use of these medications (under the ongoing care of their hepatologist) during the study. Metformin use is not allowed as it will confound assessment of glucose homeostasis. We will not ask any subject to discontinue any medication in order to participate in the study.

As we are not performing liver biopsy during the current study, the study procedures will not result in new diagnosis of NASH (which requires histology). However, subjects without known NAFLD who demonstrate $\geq 5\%$ liver fat on MRS and who have elevated ALT or AST are likely to have NASH, and, if not already under the care of a hepatologist, these subjects will be offered a clinical referral to pediatric hepatology. Subjects who are found to have labs suggesting significant liver disease (AST or ALT > 2.5x upper limit of normal (ULN) or total bilirubin > ULN) will be encouraged to seek clinical care from a hepatologist and will not be eligible for the study. AST and ALT will be carefully monitored (0, 6, 12, 18, and 24 weeks).

VIII. Potential Benefits

Participants will receive information about their nutritional and metabolic health. In addition, subjects randomized to Norditropin may experience benefits from this treatment including decrease in fat mass and possibly decreases in liver fat and systemic inflammation. All subjects will receive lifestyle counseling and information about healthy nutrition and physical activity. Further, the information obtained from this study will inform the potential use of rhGH and possibly other strategies to treat NAFLD in adolescents.

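### Aim 2a: discontinuation for a confirmed fasting glucose of 126 mg/dL or more leaves week-24 glucose values missing or off drug, which leans the result towards 'neutral', and no analysis is stated for it

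*Combined protocol and SAP*

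**What the plan says.** Aim 2a (section II) states the criterion: "Fasting and 2-hour glucose, HOMA-IR, and Matsuda index will not be significantly different from baseline after 24 weeks of Norditropin treatment". No margin is given.

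The individual rule appears in section VI (Study Drug), in section VIII under growth hormone, and in the stopping rules. In section VIII it reads: "any subject with a fasting blood sugar ≥ 126 mg/dL that is confirmed on recheck will be discontinued from the study". The study as a whole stops if "More than 2 individuals in the GH group have persistent fasting glucose ≥ 126 mg/dL".

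On follow-up, section V asks subjects who stop treatment for any reason to keep attending the visits of their randomized arm. On reversibility, section VIII says: "When side effects, including hyperglycemia, do occur with rhGH, these resolve with discontinuation of treatment", with an exception for a cause unrelated to GH.

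On measurement, section V schedules fasting glucose at weeks 2, 4, 6 and 18 in Norditropin subjects only, and at week 12 in both arms. The list in section VIII leaves out week 18. Insulin and the oral glucose tolerance test are done only at baseline and week 24.

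On analysis, section VII sets intention-to-treat on all available data. "Changes in variables measured only at baseline and 6 months" are compared between arms by a two-sample t-test. Variables with three or more timepoints go to a linear mixed model; glucose is not among the examples. Multiple imputation is optional, with no trigger or model. Nothing says how values after a glucose discontinuation are treated.

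**The concern.** The variable that Aim 2a judges is the variable that ends treatment. A subject with a large fasting rise is taken off drug before the week-24 reading. That reading then lacks the subject, or includes a value from which the effect may have gone. Both errors point towards no change.

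A comparison with the untreated arm does not remove this. The rule is worded for any subject, but four of the five interim checks are scheduled in the Norditropin arm only, and a drug-induced rise can occur only there.

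Aim 2a is a safety claim, and section I says that further studies in the pediatric age group are intended if this pilot shows benefit. A subject stopped for hyperglycemia could help the drug to look neutral.

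**Working it through.** **Inputs from the documents.** 24 subjects, where "will be randomized in a 1:1 ratio to Norditropin vs. no treatment" gives about 12 on Norditropin; 19 evaluable; two-sided alpha 0.05; individual threshold 126 mg/dL with a confirming draw; study stop at more than 2 in the GH group.

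**Inputs not in the documents (assumed).** Mean and SD of baseline fasting glucose, mean and SD of the rise on drug, within-subject SD 5 mg/dL, and return to baseline after stopping.

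**1. The plan's own figure.** None is given for Aim 2a. For secondary variables in general, section VII states 80% power at about 1.4 SD. With 9 and 10 per arm, the noncentrality is 1.4 × √(9 × 10 / 19) = 3.05 on 17 degrees of freedom, giving 81.9% (79.6% with 9 and 9). The figure reproduces. The within-arm comparison of Aim 2a needs a change of 0.89 SD for 80% power in 12 subjects.

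**2. What each measure has if a subject is discontinued.**

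| Measure | On-drug values before stopping | Week 24, subject leaves | Week 24, subject returns |
|---|---|---|---|
| Fasting glucose | Yes, serial | Missing | Off drug |
| 2-hour glucose | None | Missing | Off drug |
| HOMA-IR | None (no interim insulin) | Missing | Off drug |
| Matsuda index | None | Missing | Off drug |

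**3. How often it could happen.** With per-subject risk p, the chance of at least one among 12 is 1 − (1 − p)^12. For p = 2%, 5%, 10% and 20% this is 22%, 46%, 72% and 93%. The chance of three or more, which would stop the study, is 0.2%, 2%, 11% and 44%.

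**4. Direct arithmetic.** Let k of 12 rise by D and the rest by a. The true mean is (kD + (12 − k)a)/12. With the k subjects missing it reads a; with them back at baseline it reads (12 − k)a/12. Take D = 25 and a = 3 mg/dL:
- k = 1: true (25 + 33)/12 = 4.8; missing 3.0; off drug 33/12 = 2.75.
- k = 2: true (50 + 30)/12 = 6.7; missing 3.0; off drug 30/12 = 2.5.

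**5. Simulation of the week-24 fasting change, without the mixed model.** 12 treated subjects, five checks each with a confirming draw; mean change in mg/dL.

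| Baseline (SD); rise (SD) | Stopped | All on drug | Stopped missing | Stopped off drug |
|---|---|---|---|---|
| 90 (8); 5 (5) | 0.1% | 5.00 | 4.99 | 4.99 |
| 95 (10); 10 (15) | 13% | 9.11 | 6.97 | 6.33 |
| 97 (11); 5 (10) | 7% | 5.0 | 4.1 | 3.8 |
| 97 (11); 5 (15) | 12% | 5.0 | 2.3 | 2.0 |

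The first two rows leave out runs with three or more stopped; the last two do not. In the last row 16% of runs have three or more stopped. Without them the means are 4.3, 2.3 and 2.1, a loss of 1 − 2.3/4.3 = 47% or 1 − 2.1/4.3 = 51%. In the second row the chance that a paired test is significant falls from 0.43 to 0.30 (missing) or 0.28 (off drug).

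**6. Fasting glucose in a mixed model.** Same assumptions as the last two rows, with variances taken as known and the rise constant after baseline. With values up to stopping only, the estimate is 5.04 (true 5.06) at SD of rise 10 and 5.06 (true 5.07) at SD 15. If off-drug week-24 values are also entered, it is 4.8 and 4.2.

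**The case against.** The strongest objection is that the plan already has a suitable method for fasting glucose. It is measured at three or more timepoints in both arms, so it meets section VII's condition for the mixed model. Stopping depends on recorded glucose, so a model that uses the values up to stopping removes nearly all the bias (step 6). This stands. What stays open is whether Aim 2a, worded as change from baseline, uses that model, and whether off-drug values enter it.

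The sizes are also soft. All the simulated figures are for fasting glucose, the best protected measure, and none can be derived for the other three. An SD of rise of 15 around a mean of 5 implies that 37% of treated subjects' glucose falls. With a baseline of 90 the bias is nil. Section VIII reports no significant GH-related side effects in the pilot. These are secondary endpoints in a pilot of 24, and the DSMB would see such discontinuations. All of this limits the size and leaves the direction as it is.

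A reader might infer that the rule removes every treated subject whose glucose rises. It does not: only a confirmed fasting value of at least 126 mg/dL triggers it. Smaller rises, and worsening confined to 2-hour glucose or insulin resistance, stay in. Nor do the documents support saying that the rule acts in one arm only, since it covers any subject and both arms are checked at week 12.

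**Conclusion.** The concern holds in a limited form. Discontinuation depends on the outcome that Aim 2a judges, no handling is stated, and either reading of the follow-up text leans the week-24 result towards 'neutral' if any subject meets the rule. Reconciling section V with sections VI and VIII is necessary, but does not by itself repair Aim 2a.

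The exposure is real for 2-hour glucose, HOMA-IR and Matsuda index, and conditional for fasting glucose. For fasting change read at week 24 without the mixed model, the loss runs from nil (baseline 90, SD 8, rise 5, SD 5) to about half of the true change (baseline 97, SD 11, rise 5, SD 15). The upper end comes from wide assumed heterogeneity and should not be taken as the expected bias. About 2 of 12 treated subjects can be affected in a study that runs to completion. That limit is approximate, because the study-level rule speaks of persistent values and the individual rule of confirmed ones.

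**What to change.** Leave the stopping rule as it is and add the following to Aim 2a and section VII.

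1. For 2-hour glucose, HOMA-IR and Matsuda index, compare arms with a rank test that gives the worst rank to any subject discontinued for a confirmed fasting glucose of at least 126 mg/dL (for Matsuda, the lowest sensitivity). Make this at least a pre-specified sensitivity analysis.
2. For fasting glucose, name the planned mixed model as the analysis. Use values up to stopping, including the triggering value and its repeat draw, and show off-drug values separately.
3. Report the number meeting the rule in each arm beside the week-24 result, and do not conclude 'neutral' from the week-24 values without taking that number into account.
4. Reconcile the text on whether a glucose discontinuation ends follow-up or treatment only, and on whether fasting glucose is checked at week 18.

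The cost is a few sentences and no new data. The small downside is that the glucose result may look less favourable.
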